The navigator will enter a description of each participant's screening plan into the DCP, will print out a 1-page summary of the decision counseling session and screening plan, and will send to a copy this form to the participant. Importantly, primary care practices included in this study share an electronic medical record that includes a "progress note" feature, to which the navigator will have access. The navigator will use this feature to enter the participant's CRC screening plan directly into the electronic medical record, along with information on scheduled appointments and test performance. When the plan is entered, it will be routed to both the patient's primary physician and the practice office manager to authorize any necessary insurance referral(s), and send the referral(s) directly to the navigator and participant. The navigator will contact the office manager to verify provider receipt of the screening plan and obtain any needed referrals. At 45 days after random assignment, research staff will send participants a reminder that includes a provider endorsement and encouragement of screening. Note: the grant will cover the cost of the mailed SBT kit and, LVHN will help participants with limited or no insurance coverage by providing colonoscopy and follow-up, including treatment, at little or no cost via Medical Assistance applications and an established Charity Care program.

At 6 months after randomization, the navigator will use the same progress note feature in Centricity to provide the provider and office manager of the participant's primary care practice a participant CRC screening status report. This report will be based on screening data obtained by project staff from the 6-month survey and medical records review described below. The report will indicate whether the participant adhered to screening, and if the participant is in need of diagnostic follow-up for an abnormal SBT result. For those participants who are nonadherent to

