CRC screening, the report will advise providers and the office manager to contact the participant and encourage screening. For those screenees who require follow-up of an abnormal SBT result, the report will also encourage providers to arrange a diagnostic colonoscopy. For patients who had a normal SBT result, the report will encourage providers to contact patients in a year to offer screening. Finally, 30 days after the screening status report is mailed, the navigator will contact the office manager to verify provider receipt of the screening status report and to record follow-up action(s) taken.

Six-Month Survey and Medical Records Review. Six months after randomization, a survey interviewer from Survey Technology and Research (STR), a professional survey company, will contact each participant by telephone and administer a 6-month Survey. The survey will include items that assess participant sociodemographic characteristics. In addition, items will be included on the survey to assess CRC screening decision stage and screening test preference. In terms of actual screening adherence, survey respondents will also be asked to report any CRC screening tests performed during the 6 months. For all reported tests, participants will be asked to provide a date of testing. Following prior studies, we will allow for 20% missing survey data.

A 6-month medical records review for DSNI Group participants will be completed by a study research assistant. Screening adherence data collected on the 6-month survey and 6-month medical records review will be used to prepare the DSNI Group screening status report described earlier, and to assess the CRC screening outcome. Participant insurance status will also be ascertained on medical records review. CRC screening adherence will reflect performance of any ACS or USPSTF guidelines-recommended CRC screening test recorded in the chart or self-reported on the survey, if the survey report is accompanied by a procedure date that falls within the 6-month study period following randomization.

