Twelve-Month Medical Records Review. At 12 months after randomization, an endpoint medical records review will be performed on all study participants to assess CRC screening adherence. The medical records review will be conducted by a study research assistant who will be blinded to each participant's study group assignment. Any ACS or USPSTF guidelines-recommended CRC screening test will be accepted. Following prior studies, we will allow for 5% missing endpoint medical records data. As part of the records review, we will review electronic medical records for all participants in the last year of the study to characterize patterns of screening use among participants after the study observation period. This information will be combined with self-reported CRC screening from the 6-month survey and 6-month medical records review to determine the main study outcome in the analyses.

Follow-up Focus Groups:

In the last year of the study, the research team will also work with the OHCHD to conduct two focus groups with DSNI Group participants. The two focus groups will include screenees (n=10) and nonscreeners (n=10). We will develop discussion guides for use in eliciting participant perceptions about intervention contacts, and barriers to and facilitators of screening. Focus groups will be conducted in Spanish or English, as needed, and will be audio recorded.

Evaluation:

The research team will apply the Reach, Effectiveness, Adoption, Implementation, and Maintenance (RE-AIM) framework. We will complete an assessment of RE-AIM dimensions at different levels of the LVHN for the interim and final reports to the sponsor.

c. Data analysis: Provide the methods by which the study objectives/aims will be assessed or measured, i.e., statistical analysis plan, qualitative research methods such as procedures for conducting theme analysis and enhancing validity, program evaluation methods and analysis plan, or mixed methods analysis plan. For a quantitative study include what statistical tools will be applied and how the study is powered, if appropriate. Pilot studies do not require a statistical plan.

Preliminary Focus Groups

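### The 12-month records reviewer is said to be blinded, but the chart under review holds navigator entries made only for the DSNI arm, and no rule keeps them from the reviewer or out of the outcome

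*Combined protocol and SAP*

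**What the plan says.** **Blinding.** Part A item 4b, Twelve-Month Medical Records Review: "The medical records review will be conducted by a study research assistant who will be blinded to each" participant's group. Nothing says how. The data-source table in Part A item 7 names the EMR as the source for the 6- and 12-month reviews.

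**What the navigator puts in that record.** Under Intervention Implementation (item 4b), in the DSNI procedures, the navigator uses a progress-note feature to enter the "CRC screening plan directly into the electronic medical record, along with information on scheduled appointments and test performance". At 6 months "the navigator will use the same progress note feature in Centricity to provide the provider and office manager" a status report on whether the participant was screened. On its content: "This report will be based on screening data obtained by project staff from the 6-month survey and medical records review described below". The Six-Month Survey section ties this report to the DSNI group. The text also speaks of "30 days after the screening status report is mailed", so its route is described in two ways. No matching entry is described for SI.

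**What counts as screened.** The Six-Month Survey section accepts any guideline "CRC screening test recorded in the chart or self-reported on the survey, if the survey report is accompanied by a procedure date" within the 6-month study period. The date condition is attached to the survey report. The 12-month section accepts any guideline test and sets no source requirement.

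**The 6-month records review.** The Six-Month Survey section says: "A 6-month medical records review for DSNI Group participants will be completed by a study research assistant". The 12-month section has information "combined with self-reported CRC screening from the 6-month survey and 6-month medical records review to determine the main study outcome". Figure 1, however, shows a 6- and 12-month review in both arms, and the Aim 1 text in item 4c takes screening status from the 6-month survey and the 12-month review only.

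**The concern.** Overall screening adherence is the first primary objective, and blinded record review is the safeguard the plan offers for measuring it. Three things weaken that safeguard.

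- The navigator's entries identify the arm to anyone who opens a DSNI chart.
- If a navigator entry alone can establish that a test was done, one arm has a source of positive outcomes that the other lacks. The status report makes this concrete. It draws partly on the 6-month survey, so a DSNI self-report could pass into the chart and count as chart evidence, without meeting the date condition set for survey reports. SI has no such path.
- If a 6-month chart review is done for DSNI only and feeds the outcome, DSNI charts are searched twice and SI charts once.

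An extra evidence source in DSNI would favour DSNI. The direction of any error from an unblinded reviewer is unknown.

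**Working it through.** **1. The plan's own figure.** Inputs from item 4c, Power for Aim 1: 30% versus 45%, N = 380 (190 per arm), two-sided alpha 0.05.

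Power = Φ[(Δ − 1.96·se0)/se1], with se0 = √(2·p̄(1−p̄)/n) and se1 = √([p1(1−p1) + p2(1−p2)]/n).

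- se0 = √(2 × 0.375 × 0.625/190) = 0.0497
- se1 = √((0.21 + 0.2475)/190) = 0.0491
- Power = Φ[(0.15 − 0.0974)/0.0491] = 85.8%

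The stated 85% is reproduced. Nothing in the power statement needs correcting.

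**2. Blinding: the text side by side.** The reviewer is blinded (12-month section). The reviewer reads the EMR (item 7). The EMR holds DSNI-only entries (Intervention Implementation). Part B item 5 limits operations data, including group assignment, to authorized personnel, but does not address notes in the chart. It also mentions study-specific chart audit forms, whose content is not given. No statement separates the reviewer from the entries.

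**3. The 6-month records review.**

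| Place | Arms | Feeds the outcome? |
|---|---|---|
| Figure 1 | both, 190 complete in each | not stated |
| Six-Month Survey section | DSNI | yes |
| Twelve-Month section | not stated | yes |
| Item 4c, Aim 1 | not applicable | not listed; survey and 12-month review only |
| Item 4c, Evaluation; item 7 | no arm restriction | used for effectiveness in Evaluation |

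These statements cannot all describe one procedure.

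**4. Size of the evidence route (illustration).** From the documents: 190 per arm; 20% stool blood test (SBT) and 10% colonoscopy in SI (Power for Aim 3), so 19 SI colonoscopies. Assumed: the same true 30% in both arms; SBT fully captured by the laboratory; a share u of colonoscopies with no other chart record and no qualifying survey report; navigator notes recover 85% of these in DSNI. The test is an unadjusted pooled z-test, which simplifies the planned logistic model.

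SI observed = 0.30 − 0.10u. DSNI observed = 0.30 − 0.10u × 0.15.

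Rejection probability = Φ[(Δ − 1.96·se0)/se1] + Φ[(−Δ − 1.96·se0)/se1].

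| u | SI tests missed (19u) | SI observed | DSNI observed | Gap, points | Odds ratio | Type I error |
|---|---|---|---|---|---|---|
| 5% | 0.95 | 29.50% | 29.93% | 0.425 | 1.02 | 5.1% |
| 10% | 1.9 | 29.00% | 29.85% | 0.85 | 1.04 | 5.4% |
| 20% | 3.8 | 28.00% | 29.70% | 1.70 | 1.09 | 6.5% |

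Exact binomial enumeration gives 5.2%, 5.4% and 6.6%, against 5.07% with no gap. If recovery in DSNI were complete, gaps of 0.5, 1 and 2 points would give 5.1%, 5.5% and 7.1%. The 20% row is a high case: it matches every colonoscopy among the 20% expected survey non-respondents (19 × 0.20 = 3.8) also lacking any other chart record.

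This sizes missed SI tests only. It does not size reviewer unblinding, or undated self-reports passing through the status report. The documents give no rate for either.

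**The case against.** The best defence is that this is an IRB form that asks for a brief description. Rules on which notes count would normally sit in the chart audit form, which is not supplied and may already contain them. The mitigating facts are also real. SBT results come directly from a centralized laboratory, dated survey reports count in both arms, the status report rests on survey and chart data that largely count already, and whether a test was done leaves a reviewer little discretion. All of this stands. It lowers the importance and the confidence on the evidence question. It does not answer the blinding question, because the plan makes the claim and describes entries that undercut it.

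Three stronger readings are tempting, and the documents do not support them.

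- *The 6-month review is settled as DSNI-only and as part of the primary outcome.* Two sections say so, but Figure 1 and the Aim 1 text point the other way. The supportable finding is inconsistency.
- *The 85% is the plan's own recovery rate.* The plan expects navigation to be delivered to about 85% of DSNI participants. It does not say how navigators learn of completed tests, or how many otherwise unrecorded tests they would document. Here 85% is purely an assumption.
- *The bias could be large.* If 10% of unscreened DSNI participants were wrongly counted as screened, with true rates of 30% in both arms, type I error would be about 30%. That needs 0.10 × 0.70 × 190 = 13.3 people, and no passage suggests such a rate. Similarly, a 5-point deficit in SI would be 9.5 of its 19 expected colonoscopies, or half.

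**Conclusion.** The concern holds as a minor one. On the text, the stated blinding is not secured, and navigator entries are not ruled out as outcome evidence. Confidence is high on the first and lower on the second, because the audit form is unseen. The status of the 6-month records review is contradictory and must be reconciled.

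Under the assumed inputs, type I error moves from 5% to about 5.1% to 6.5%, with a gap of at most 1.7 points against a planned difference of 15. The effect of unblinding itself cannot be sized.

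A reader might infer that the reviewer will in fact be unblinded, or that the Aim 1 result is biased towards DSNI. The documents show only that the plan does not prevent either. They do not show that it happens, and this is not a threat to the main conclusion.

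**What to change.** 1. State that navigator progress notes and status reports alone are not outcome evidence in any records review that feeds Aim 1.
2. Have the 12-month reviewer abstract from laboratory, procedure and non-navigator provider records, with navigator entries excluded, and write this on the chart audit form. Deleting the blinding statement would be simpler, but it would give up the safeguard.
3. Require a test date within the 12-month window for chart evidence, in both arms alike.
4. Reconcile Figure 1, the Six-Month Survey section, the Twelve-Month section and the Aim 1 text, so that Aim 1 uses the same records reviews in both arms.

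**Cost.** A revised audit form, a short abstraction instruction and some set-up to filter the record. A test known only from a navigator note would no longer count. Provider notes may still mention the navigator, so masking is improved but not guaranteed.

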Aim 1 (DSNI versus SI on overall CRC screening adherence). The two study groups will be compared in terms of the fraction of participants who undergo CRC screening (through SBT, colonoscopy, flexible sigmoidoscopy, etc.) within 12 months of the randomization date. Screening status will be determined using both the 6-month survey and 12-month medical records review data. We hypothesize that DSNI Group participants will have higher overall screening than SI Group participants. We will analyze screening (yes vs. no) via logistic regression, using study group (DSNI versus SI) as the main predictor. As mentioned above, we expect the two study groups to be comparable at baseline due to randomization. So, the model will control only for practice and participant gender and age (the latter two variables will be included to allow addition of interaction between study group and gender or age in secondary analyses). If, however, substantial baseline imbalances occur, the model will include for those additional variables.

Aim 2 (DSNI versus SI on change in CRC screening decision stage). CRC screening decision stage will be assessed in both the baseline and 6-month surveys. Forward change (between baseline and endpoint) will encompass any movement from a lower to a higher decision stage. We hypothesize that DSNI Group participants will have greater forward movement in screening decision stage than SI Group participants. We will analyze forward change in screening decision stage (yes vs. no) via logistic regression. These analyses will be based on 6-month survey data. Prior research suggests that survey response will be comparable in both study groups. The model will include practice and participant baseline characteristics.

Aim 3 (DSNI versus SI on test-specific CRC screening adherence). The two study groups will be compared in terms of the fraction of participants who undergo a SBT or a colonoscopy within 12 months. Due to current screening practices in primary care, we expect very few, if any, instances of screening via other modalities. We hypothesize that DSNI Group participants will have higher SBT and colonoscopy screening than SI Group participants. The main analysis of test-specific screening (no screening, SBT screening, colonoscopy screening) will be based on polytomous (multinomial) logistic regression. The analysis strategy will be similar to that for Aim 1 (i.e., control for practice, as well as participant gender and age).

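### The procedures text sets a source rule for the main screening outcome that conflicts with the 12-month Aim 1 definition: read literally, it admits tests after month 12 and a 6-month records review described for one arm only.

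*Combined protocol and SAP*

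**What the plan says.** All references are to Part A of the combined protocol and SAP.

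- **4c, Aim 1.** The outcome is the proportion of participants screened "within 12 months of the randomization date". Two sources are named: "Screening status will be determined using both the 6-month survey and 12-month medical records review data".
- **4b, Twelve-Month Medical Records Review.** The paragraph opens with the endpoint review: "At 12 months after randomization, an endpoint medical records review will be performed on all study participants to assess CRC screening adherence". It then describes a further look at every participant's electronic records, "in the last year of the study to characterize patterns of screening use among participants after the study observation period". The next sentence reads: "This information will be combined with self-reported CRC screening from the 6-month survey and 6-month medical records review to determine the main study outcome".
- **4b, Six-Month Survey and Medical Records Review.** The 6-month records review is described for DSNI participants, and its data are to serve both the DSNI status report and the screening outcome. A self-reported test is accepted "if the survey report is accompanied by a procedure date that falls within the 6-month study period following randomization". That sentence puts no date limit on tests found in the chart.
- **Figure 1.** Records review at 6 and 12 months is shown for both arms.
- **4c, Additional Analyses.** Screening beyond the first 12 months is to be described, separately from Aim 1.
- **4c, Evaluation.** For effectiveness on the primary outcomes, three sources are listed: the 6-month survey, the 6-month records review and the 12-month records review.

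**The concern.** The procedures and the analysis section each say how the main outcome is built, and they do not agree. There are two separate mismatches.

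**Time.** The sentence that builds the outcome opens with a pronoun whose nearest antecedent is the last-year review. An analyst who follows it as written would count tests performed after month 12. The last year is fixed on the study calendar, so participants enrolled early would have more time to be counted than those enrolled late. Randomization should balance this between arms, but the result would be a rate over mixed follow-up lengths, not a 12-month rate.

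**Sources.** The same sentence brings in the 6-month records review. If that review is done only in the DSNI Group, as the procedures describe, one arm has an extra chance of being recorded as screened.

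The two could act in opposite directions. Late catch-up screening at a similar pace in both arms would narrow the difference, while an extra DSNI-only source would widen it. A rule that can be read either way also leaves room to choose once the data have been seen.

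**Working it through.** **1. Candidate rules side by side**

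| Place | Time limit on counted tests | Sources for the main outcome |
|---|---|---|
| 4c, Aim 1 | 12 months | 6-month survey, 12-month review |
| 4b, Twelve-Month Review, literal reading | none stated | last-year records, 6-month survey, 6-month review |
| 4b, Twelve-Month Review, charitable reading | 12 months | 12-month review, 6-month survey, 6-month review |
| 4c, Evaluation | none stated | 6-month survey, 6-month review, 12-month review |

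The charitable reading takes the pronoun to mean the 12-month endpoint review. It removes the conflict over time but not the one over sources, because the 6-month review is still added to the Aim 1 list.

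**2. Reproducing the plan's power**

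Inputs (4c, Sample Size and Power; Power for Aim 1): p1 = 0.30 (SI), p2 = 0.45 (DSNI), N = 400 × 0.95 = 380, so n = 190 per arm, two-sided alpha 0.05, stated power 85%.

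Power = Φ{ [Δ − 1.96·√(2p̄(1−p̄)/n)] / √([p1(1−p1) + p2(1−p2)]/n) }

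- Δ = 0.15 and p̄ = 0.375.
- √(0.46875/190) = 0.0497, and 1.96 × 0.0497 = 0.0974.
- √(0.4575/190) = 0.0491.
- (0.15 − 0.0974)/0.0491 = 1.07, which gives 85.8% from unrounded values.

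The stated 85% reproduces.

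**3. Illustration of counting later tests**

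The documents give no uptake rate after month 12. Assume that a share h of those unscreened at 12 months, the same in each arm, is later screened and counted. Each rate becomes p + (1 − p)h, and the difference becomes 0.15 × (1 − h).

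| h (assumed) | SI | DSNI | Difference | Power |
|---|---|---|---|---|
| 0% | 30.0% | 45.0% | 15.0 points | 86% |
| 5% | 33.5% | 47.8% | 14.25 points | 81% |
| 10% | 37.0% | 50.5% | 13.5 points | 76% |
| 20% | 44.0% | 56.0% | 12.0 points | 65% |

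The loss depends on the equal-share assumption. If instead the odds ratio stays at (0.45/0.55)/(0.30/0.70) = 1.91 while the SI rate rises from 30% to 50%, power stays between 86% and 88%.

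**4. The one-arm source**

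Each DSNI participant recorded as screened only through the 6-month review adds 1/190 = 0.53 percentage points to the DSNI rate, with no SI counterpart. The documents do not say how many there would be. A complete 12-month review of the same records should find most of these tests. The room for asymmetry is therefore mainly where the 12-month review is missing: 5% of 200, or 10 participants per arm, on the plan's own allowance.

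**The case against.** The strongest reply is that the plan defines Aim 1 explicitly as a 12-month outcome, and that the rest of the document shows what the loose pronoun means. The paragraph is about the 12-month review. The last-year look has its own descriptive purpose. Additional Analyses treats later data as descriptive. The source list under Evaluation matches the disputed sentence with the 12-month review in place of the pronoun. Neither Figure 1 nor the data-source table in item 7 shows last-year records as a separate source. All of this stands, and it makes 12 months the evident intent.

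A reader might go further and infer three rival windows (6 months, 12 months and open-ended). The documents do not support that. The 6-month limit decides which dated self-reports on the 6-month survey are accepted, and it is compatible with a 12-month outcome. Calling this interval the study period is loose, and a self-report dated shortly after month 6 would be refused although it falls inside the Aim 1 window. That calls for alignment but does not create a second endpoint.

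A reader might also infer that the Aim 1 rate is not the 12-month rate the trial was powered on. That does not follow either. The only explicit Aim 1 definition is 12 months, and the power paragraph attaches no window to 30% and 45%.

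The reply does not dispose of the point. The procedures are not silent: they state how the main outcome is determined. The Evaluation list repeats the extra 6-month source and so does not resolve the mismatch.

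**Conclusion.** The concern holds as a conflict between passages, and it should be corrected before the outcome dataset is built. Followed literally, the procedures could count tests after month 12 over unequal follow-up and could use different outcome sources in the two arms. The intended window is very probably 12 months, so this is not evidence that the trial has a different endpoint or is underpowered.

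The size cannot be derived from the documents. The fall from about 86% to between 81% and 65% rests wholly on assumed late uptake of 5% to 20%, equal in both arms. Under a constant odds ratio there would be no loss. The effect of a DSNI-only 6-month review is likewise unknown. It would favour DSNI, and it may be small if the 12-month review is nearly complete.

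**What to change.** - **4b, Twelve-Month Review:** replace the opening pronoun of the disputed sentence with an explicit reference to the 12-month endpoint records review, and remove the 6-month records review as an outcome source.
- **State one rule:** the Aim 1 outcome counts any accepted test dated from randomization to 12 months, taken from the 6-month survey and the 12-month records review, with the same sources in both arms. Survey self-reports must stay in, because Aim 1 names them.
- **4b, Six-Month section, and 4c, Evaluation:** align both with Aim 1. The DSNI 6-month review can continue to feed the status report. Bring the self-report date condition into line with the 12-month window, and reconcile Figure 1 with the text on which arms have a 6-month review.
- **Chart audit form:** require the test date to be abstracted. The plan asks survey respondents for dates but does not expressly say that chart dates are recorded.
- **Last-year records:** use them only for the descriptive work under Additional Analyses.

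The cost is a few sentences, one field on the audit form and one date filter. The sample size and the stated power do not change.
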